**PART II**  
**CLINICAL RESEARCH PROPOSAL**

This section will be reviewed by the appropriate Clinical Review Panel. Each of the headings in this section must be addressed. Use as much space as needed.

**A. SPECIFIC AIMS OR RESEARCH QUESTIONS - answer each question individually.**

*1. What is the condition or intervention to be studied?*

Periacetabular osteotomy (PAO) is an elective reorientation surgery for the hip joint, typically for the treatment of hip dysplasia in young, otherwise healthy patients, which requires multiple pelvic osteotomies around the acetabulum [1]; a major source of its perioperative morbidity is blood loss [2]. The principal cause of postoperative blood loss after PAO is surgical trauma, with secondary activation of both the coagulation cascade and local fibrinolysis [3]. Tranexamic acid (TXA) is a synthetic derivative of the amino acid lysine that acts as competitive inhibitor of plasminogen activation, interfering with fibrinolysis [4]. Multiple studies and meta-analyses have shown that intravenous (IV) of TXA reduces postoperative bleeding and the need for transfusion after orthopedic surgery, including total joint arthroplasty, with no demonstrable change in the risk for postoperative complications, including venous thromboembolic events (VTE) [5-10]. However, there is no prospective data regarding TXA use for PAO, and, in our experience, PAO surgeons question and argue the use and disuse of TXA for this procedure.

In the PAO literature, allogeneic transfusion rates are as high as 58% [11], and blood loss can range to nearly 4 L [2, 11-17]. If autologous blood and intraoperative cell saver are considered along with allogeneic transfusions, the risk of perioperative transfusion can be as high as 94% [2].

Retrospectively, we reviewed 93 PAO cases performed by the principle investigator of this study. The average calculated blood loss was  $1.30 \pm 0.38$  L (range, 0.32 L – 2.65 L), and 33.3% of patients required at least one transfusion of allogeneic blood postoperatively. There has been one retrospective study examining the effect of IV TXA on blood loss and transfusion after PAO that showed that IV TXA may reduce total blood loss by 30.8% ( $p=0.001$ ) and transfusion rate by 58.6% ( $p=0.013$ )[11].

The goal of this randomized controlled, double-blinded trial is to assess the efficacy of IV TXA in reducing calculated total blood loss in patients undergoing PAO. Our specific objectives included analysis of (1) calculated total blood loss (primary outcome), (2) intraoperative cell saver utilization (secondary outcome), and (3) postoperative allogeneic blood transfusion (secondary outcome).

*2. What is/are the research question(s)/specific aim(s)? Pose very specific questions that can be addressed within the proposed design of the study. Prioritize them in order of importance.*

The specific aim of the study is to determine whether the use of perioperative IV TXA, given prior to incision (concurrent with preoperative antibiotics) and then at wound closure, reduces the calculated total blood loss postoperatively in patients undergoing PAO when compared to a patients receiving placebo (normal saline). A 250 mL difference in blood loss will be considered a clinically important difference [18].

Secondary objectives of the study are to study whether the use of IV TXA reduces intraoperative cell saver utilization, transfusion of allogeneic blood, and hospital length-of-stay (LOS) compared to placebo use. We will also compare complications between study groups, including the incidence of clinically apparent deep vein thrombosis (DVT) and pulmonary embolism (PE), from postoperative day zero through 6 weeks postoperatively.

3. *What is/are the hypothesis(es)?*

**Hypothesis 1:** The use of IV TXA given prior to incision and at the time of wound closure will decrease the postoperative calculated total blood loss in patients undergoing PAO compared to patients receiving placebo.

**Hypothesis 2:** Patients receiving perioperative IV TXA will have lower intraoperative cell saver utilization, lower rate of allogeneic blood transfusion, shorter hospital LOS after PAO compared to patients receiving.

**Hypothesis 3:** There will be no difference in the rate of symptomatic venous thromboembolic events (VTE) (i.e., DVT and PE) in the 6 weeks after PAO surgery in patients who receive perioperative IV TXA compared to patients receiving placebo.

4. *Identify and define the primary outcome and when the outcome will be measured. If measuring change in post-operative function is the most important, that will be your primary outcome.*

Postoperative calculated total blood loss after PAO, determined from estimated blood volume [19], change in postoperative hemoglobin (preoperative hemoglobin – final inpatient hemoglobin), and transfused hemoglobin [20,21].

5. *Identify and define the secondary outcome(s) and when they will be measured (list additional goals one at a time with their corresponding outcomes).*

Secondary outcomes:

1. Intraoperative cell saver utilization: cumulative mL of reinfusion, measured at the end of the case intraoperatively
2. Postoperative allogeneic transfusion (units of packed red blood cells per patient)
3. Length of hospital stay (postoperative day of discharge after surgery)
4. Incidence of complications at 6 weeks postoperatively, specifically:
  - VTE (symptomatic of DVT or PE)
  - Infection (superficial, deep)
  - Hematoma
  - Seroma
  - Reoperation

Patients will not be followed longer than 6 weeks during this trial, as we are aware of no evidence to suggest that TXA will influence outcomes outside of the perioperative period.

The authors will create a data safety monitoring board (DSMB) that will meet once a quarter to capture any complications, including but not limited to: death, DVT, PE, and wound complications.

This will include anesthesia, surgical, nursing, and research representatives. The time frame for reporting adverse events will be 1 week. If any mortality is seen, or any increase in DVT or PE rates from the established incidence in the literature (i.e., 0.94% for symptomatic VTE), the study will be stopped. The senior author and principal investigator will contact the IRB directly if any of the above occurs. In accordance with the Hospital guidelines for TXA use, DVT, PE, stroke, transient ischemic attack (TIA) and myocardial infarction (MI) will be reported to the Department of Quality Management ([name]).

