**D. SAMPLE SIZE AND DATA ANALYSIS**

If you are uncertain about how to calculate your sample size and determine appropriate data analysis, please contact the Epidemiology and Biostatistics Core at [[contact]](mailto:[contact]) for assistance in completing this section.

*If this is a case series based only on the patients available and only descriptive statistics will be obtained, state this in lieu of a sample size calculation. However, if you propose a case series, but plan hypothesis testing (e.g., the calculation of p-values using statistical tests) you need to estimate your*

**Sample Size – Support estimates with evidence from the literature or prior studies and perform an appropriate sample size calculation.**

Proposed analysis (e.g., student's t-test, ANOVA, chi-square, regression, etc.):

Outcome variables of interest are all continuous. Two-sample t-test and multivariate linear regression will be utilized if the data is normally distributed; otherwise Mann-Whitney U test (non-parametric equivalent to the two-sample t-test) will be utilized.

1. Alpha level: 0.05
2. Beta or power level: 0.82
3. Primary outcome variable estimate (mean +/- s.d. for continuous outcome, frequency/percentage for categorical variable):

The primary outcome will be the calculated total blood loss, summarized as mean +/- s.d. Based on historical data of patients that underwent PAO or PAO/Scope without IV TXA, the mean calculated blood loss was approximately 1296 mL with a standard deviation of 383.27 mL.

4. Number of groups being compared (use 1 for paired analysis within the same subjects):

Two groups will be compared: treatment arm (up to 1 g of IV TXA diluted in 50 mL of normal saline) versus those receiving placebo (50 mL of normal saline)

5. Effect size or change expected between groups: 250 mL difference in blood loss
6. Resulting number per group: 40 per group
7. Total sample size required: 80

**Data Analysis - describe how the primary outcome will be analyzed and what types of statistical calculations will be used. Do the same for each secondary outcome. Reiterate briefly the main analysis to be done, which groups, which variables, possible confounders. Address how possible confounders will be identified and handled in the analysis.**

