The primary outcome, calculated total blood loss, will be presented as mean +/- standard deviation and compared between the TXA and placebo arms with a two-sample t-test. Multiple linear regression will also be used to compare total blood loss volume between arms after adjustment for age, sex, BMI, and anesthesia type.

Calculated total blood loss will be determined from the difference between the preoperative hemoglobin and the lowest postoperative hemoglobin during the hospital stay (or the lowest

postoperative hemoglobin prior to transfusion). Based on hemoglobin balance, the estimated blood loss will be calculated according to the formula by Nadler et al. [19]:

$$\text{Estimated Blood Volume (EBV)} = (k_1 \times \text{Height}^3 \text{ (m)}) + (k_2 \times \text{Weight (kg)}) + k_3$$

For men,  $k_1 = 0.3669$ ,  $k_2 = 0.03219$ , and  $k_3 = 0.6041$

For women,  $k_1 = 0.3561$ ,  $k_2 = 0.03308$ , and  $k_3 = 0.1833$

Multiplying the EBV by the hematocrit (Hct) gives the red blood cell (RBC) volume. As such, a change in the RBC volume can be calculated from a change in the Hct level [20, 21]:

$$\text{Total RBC volume loss} = \text{EBV} \times (\text{Hct Preop} - \text{Hct Postop})$$

Transfusions (mean volume per unit, mL) can be taken into account by calculating the total blood loss:

$$\text{Total blood loss (L)} = \text{Total RBC volume loss} + (\text{No. of Units Transfused} \times 0.285) / (\text{Hct Preop} - \text{Hct Postop}) / 2$$

Continuous secondary outcomes (postoperative allogeneic blood transfusion, intraoperative cell saver utilization, and length of hospital stay) will be analyzed in the same manner as the primary outcome.

The incidence of complications will be reported as proportions and 95% confidence intervals.

All hypotheses will be evaluated with two-sided tests with statistical significance set at  $\alpha = 0.05$ .

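### Hypothesis 3 predicts no difference in VTE with no margin, and a two-sided test at 0.05 with 40 patients per arm cannot support it

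*Combined protocol and SAP*

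**What the plan says.** Section A, item 3 lists three hypotheses. The third concerns symptomatic VTE in the six weeks after surgery: "There will be no difference in the rate of symptomatic venous thromboembolic events (VTE". No equivalence or non-inferiority margin is given there or anywhere else, and nothing marks this hypothesis as exploratory.

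Section A, item 2 says of the same outcome: "We will also compare complications between study groups".

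Section D, Data Analysis, has two sentences that bear on it. The one specific to complications reads: "The incidence of complications will be reported as proportions and 95% confidence intervals". The general one that follows reads: "All hypotheses will be evaluated with two-sided tests with statistical significance set at" 0.05.

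The sample size (section C, item 2(c), and section D) is 40 per arm. It rests on blood loss alone: a 250 mL difference, SD 383.27 mL, "Alpha level: 0.05" and "Beta or power level: 0.82". Section D describes the outcome variables as all continuous and names no test for a binary outcome. Section B, item 1 gives the background rate of clinically significant VTE as 0.94%.

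**The concern.** A two-sided test of a difference either rejects equality or fails to reject it. When the hypothesis is that there is no difference, and no margin is set, the only test result that agrees with it is failure to reject. With a rare event and 40 patients per arm, failure to reject is close to certain whether or not the drug raises the risk. It therefore carries almost no information about Hypothesis 3.

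The two sentences in section D also do not fit together. One calls for description with intervals. The other, read literally, calls for a significance test of every hypothesis, including this one. The quantity that would inform a reader about safety, an interval for the difference between arms, is not specified, although section A says the groups will be compared.

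At stake is what the trial may say about its main named safety outcome. The primary analysis is not affected.

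**Working it through.** **Inputs.** 40 per arm, 80 in total (section D); two-sided α = 0.05 (section D); VTE rate 0.94% (section B, item 1). Assumptions: Fisher's exact test, because no binary test is named, and complete follow-up of all 80 patients.

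**1. The plan's own figure.** For blood loss, the noncentrality is (250 / 383.27) × √(40/2) = 0.652 × 4.472 = 2.92 on 78 degrees of freedom. The two-sided t-test power is 82.1%, so the stated 82% is reproduced. The plan states no such figure for VTE.

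**2. Expected events at 0.94% in both arms.**
- Per arm: 40 × 0.0094 = 0.38. In total: 80 × 0.0094 = 0.75.
- Chance of no event at all: (1 − 0.0094)^80 = 0.470, or 47%.

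**3. What a significant result would need.** When all k events fall in one arm, two-sided Fisher p = 2 × C(40,k) / C(80,k).
- k = 5: 2 × 658,008 / 24,040,016 = 0.055, not significant.
- k = 6: 2 × 3,838,380 / 300,500,200 = 0.026, significant.
- With one event in the other arm, 7 vs 1 gives p = 0.057 and 8 vs 1 gives p = 0.029.

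The smallest significant split is 6 vs 0, which is eight times the number of events expected in the whole trial (6 / 0.75).

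**4. Power of that test.** This is the sum of the binomial probabilities of all splits with p < 0.05, with the control arm at 0.94%. It assumes that all 80 patients are followed and that the VTE stopping rule is not applied.

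| True rate on TXA | Power |
|---|---|
| 1.88% (doubled) | under 0.01% |
| 2.82% (tripled) | 0.06% |
| 4.7% (five-fold) | 0.7% |
| 9.4% (ten-fold) | 12% |

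**5. What a trial with no events would show.**
- Exact 95% upper limit for 0/40: 1 − 0.025^(1/40) = 8.8%.
- Newcombe 95% interval for the difference, 0/40 vs 0/40: the Wilson upper limit is 1.96² / (40 + 1.96²) = 3.84 / 43.84 = 8.8%, so the interval is −8.8 to +8.8 percentage points.
- 8.8 / 0.94 is about 9, so even this most favourable result is compatible with an excess of about nine times the published rate.

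**6. Size needed for a formal claim.** The documents give no margin, so the margins here are assumptions. With equal true rates of 0.94%, one-sided 0.025 and 80% power, n per arm = (1.960 + 0.842)² × 2 × 0.0094 × 0.9906 / margin². This gives 1,462 for a margin of 1 point, 366 for 2, 163 for 3 and 59 for 5. The plan has 40.

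**The case against.** The strongest reply is that the plan for VTE is already descriptive. The only sentence specific to complications calls for proportions and intervals, and the tests named in section D are for continuous outcomes. On this view the all-hypotheses sentence fixes sidedness and threshold and was not meant to add a VTE test, and Hypothesis 3 merely records what the investigators expect. Much of this stands. It is why the point is minor, and why the Fisher figures must be labelled as resting on an assumed test. It does not remove the point: the general sentence covers Hypothesis 3 as written, no margin is stated, and no interval for the difference is specified.

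A reader might go further than the documents allow in four ways.

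- *That the plan will declare the drug safe if p > 0.05.* No passage says so. The practice-change claim in section B, item 4 is tied to blood loss, and the belief in safety in section B, item 1 rests on outside evidence.
- *That the plan provides intervals per arm only.* Section D does not say whether the intervals are per arm, pooled or for the difference. The specification is incomplete; it does not exclude a difference interval.
- *That the stopping rule makes a completed trial confirm Hypothesis 3.* Section A, item 5 stops the study on "any increase in DVT or PE rates from the established incidence in the literature (i.e., 0.94% for symptomatic VTE"). Read literally, one event in 80 (1.25%) already exceeds that rate. But the chance of no event in either arm is then (0.9906)^40 × (0.953)^40 = 10% under a five-fold increase and (0.9906)^40 × (0.906)^40 = 1.3% under a ten-fold increase. A large harm would usually halt the trial, not produce a reassuring completed one. The rule therefore lends this point no support.
- *That the power figures describe the trial as it would run.* They describe the test alone, in a trial that continues to 80 patients whatever happens.

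**Conclusion.** Wrong as written, and minor, because it concerns a secondary safety outcome. Hypothesis 3 is a no-difference statement without a margin, placed under a blanket rule of two-sided testing. With 40 per arm and a 0.94% rate, a non-significant result cannot support it: 0.75 events are expected in all, 6 vs 0 are needed for significance, and a trial with no events leaves about ±8.8 percentage points.

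The event counts rest on the cited rate applying to these patients. The 6 vs 0 threshold rests on Fisher's test. The ±8.8 points rest on the Newcombe method with full follow-up, and do not depend on the assumed rate. The finding is about what the trial could conclude on VTE; it does not show that the investigators intend to claim safety from a p-value.

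**What to change.** Four changes of wording:

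1. In section A, item 3, restate Hypothesis 3 as a descriptive safety objective: to estimate symptomatic VTE in each arm through six weeks.
2. In section D, exempt it from the sentence that puts all hypotheses under two-sided tests.
3. In section D, specify VTE counts per arm with exact 95% confidence intervals, and a 95% confidence interval for the risk difference by a named method that remains valid with zero events, such as Newcombe's.
4. State that 80 patients cannot establish absence of a difference in VTE, and that a non-significant comparison will not be taken as evidence of one.

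Sample size, procedures and data collection do not change. The cost is that the trial gives up a no-difference claim that it could not have supported. If the sponsor wants to keep such a claim, it needs a pre-specified margin and a trial sized for it.

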**Data recorded from the electronic medical record will include:**

- Date of surgery
- Patient age at the time of surgery
- Patient gender
- Patient height (cm) and weight (kg) at time of admission

- Transfusion requirement during inpatient stay (units required)
- Postoperative day and time of discharge
- Preoperative CBC data and coagulation study data
- Postoperative hemoglobin on all inpatient days postoperatively (g/dL)
- Chart review of progress notes for evidence of clinically significant VTE
- Chart review of progress notes for evidence of reoperation, hematoma, seroma, or postoperative infection

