**Data recorded from the operating room record will include:**

- Anesthetic used (e.g., regional, general, etc.)
- Operative times (minutes)
- Intraoperative transfusion requirements (units of blood)
- Use of cell saver intraoperatively (autotransfusion volume, mL)

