Form 1 -Clinical Research Proposal Form

$$\text{Estimated Blood Volume (EBV)} = (k_1 \times \text{Height}^3 \text{ (m)}) + (k_2 \times \text{Weight (kg)}) + k_3$$

For men,  $k_1 = 0.3669$ ,  $k_2 = 0.03219$ , and  $k_3 = 0.6041$

For women,  $k_1 = 0.3561$ ,  $k_2 = 0.03308$ , and  $k_3 = 0.1833$

Multiplying the EBV by the hematocrit (Hct) gives the red blood cell (RBC) volume. As such, a change in the RBC volume can be calculated from a change in the Hct level [20, 21]:

$$\text{Total RBC volume loss} = \text{EBV} \times (\text{Hct Preop} - \text{Hct Postop})$$

Transfusions (mean volume per unit, mL) can be taken into account by calculating the total blood loss:

$$\text{Total blood loss (L)} = \text{Total RBC volume loss} + (\text{No. of Units Transfused} \times 0.285) / (\text{Hct Preop} - \text{Hct Postop}) / 2$$

The rate of perioperative blood transfusions, both intraoperative and postoperative, will be documented for analysis.

The criteria for transfusion of blood products will be a hemoglobin level of  $< 8.0$  g/dL or a hemoglobin level of  $< 10.0$  g/dL with clinical signs of symptomatic anemia (e.g., chest pain that was deemed to be cardiac in origin, congestive heart failure, unexplained tachycardia, or hypotension unresponsive to fluid replacement). Blood will be administered 1 unit at a time, and the presence of symptoms or signs will be reassessed. Of note, the chart of the patient will clearly indicate him/her as a study patient.

VTE prophylaxis will be standardized, with each patient receiving 3 weeks of prophylaxis with 325 mg of oral aspirin twice daily. All patients will also receive a comprehensive, multidisciplinary approach to postoperative care with mechanical (sequential compressive device) prophylaxis in-house, early mobilization with physical therapy, medical optimization, and regional anesthesia, if appropriate.

**4. What is the long-term significance? - state the potential long-term benefits of the study, why it is important and its potential significance.**

The risk of excessive blood loss and blood transfusion in young, healthy patients after elective surgery is an event that can be reduced with blood conservation protocols, which can include pharmacological agents like TXA. If the use of IV TXA in the PAO patient population significantly reduces total perioperative blood loss, then it would provide an efficacious and inexpensive method for reducing postoperative morbidity after PAO.

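### The tested transfusion outcome is labelled postoperative units only, which is narrower than the secondary objective and Hypothesis 2; define it as total perioperative allogeneic units

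*Combined protocol and SAP*

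**What the plan says.** The question is asked without a time window. The secondary objectives in A.2 ask whether TXA "reduces intraoperative cell saver utilization, transfusion of allogeneic blood, and hospital length-of-stay (LOS", and Hypothesis 2 in A.3 predicts a "lower rate of allogeneic blood transfusion, shorter hospital LOS after PAO".

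The outcome has a window. A.5 lists "Postoperative allogeneic transfusion (units of packed red blood cells per patient". The Outcome Measures list in C.3(g) uses the same postoperative label, and the Data Analysis text in section D reads "Continuous secondary outcomes (postoperative allogeneic blood transfusion, intraoperative cell saver utilization, and length of hospital stay) will be analyzed" in the same way as the primary outcome, that is, by two-sample t-test and linear regression. The closing paragraph of A.1 also words the objective as postoperative.

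The data cover both periods. The operating room list in C.3(b) includes "Intraoperative transfusion requirements (units of blood", and the electronic record list includes "Transfusion requirement during inpatient stay (units required". Below the blood-loss formula in C.3(g), the plan adds: "The rate of perioperative blood transfusions, both intraoperative and postoperative, will be documented for analysis".

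**The concern.** The first dose is given before incision, so blood given in theatre afterwards is a possible consequence of treatment. A transfusion outcome that starts only after surgery leaves it out. Under a literal reading, a patient who bleeds heavily and receives bank blood only in theatre has the same score, 0 units, as a patient who never needed blood.

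The two periods are also linked. The transfusion criteria in C.3(g) depend on the hemoglobin level. A unit given in theatre raises hemoglobin and so can lower the chance of meeting those criteria on the ward. The postoperative count then depends partly on an earlier post-dose event that the specified transfusion comparison does not include.

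What is at stake is whether the reported comparison matches Hypothesis 2 as worded, and whether the absolute difference in units is somewhat too small. There is a reporting risk too. With two candidate windows in the text, the choice between them could be made after the data are seen.

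**Working it through.** **1. The plan's own figure.** The only sample-size figure is for calculated blood loss: 40 per arm, difference 250 mL, SD 383.27 mL, two-sided alpha 0.05, stated power 82% (C.2(c) and section D).

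- Standard error = 383.27 × √(2/40) = 85.70 mL; 250/85.70 = 2.917.
- Power by normal approximation = Φ(2.917 − 1.960) = 83.1%; by noncentral t, 82.1%.

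The figure reproduces and does not depend on how transfusion is defined. No power is stated for the transfusion outcome.

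**2. What the literal endpoint omits.** For mean units per patient, total difference = postoperative difference + theatre difference. The tested outcome captures the first term only. The second term is zero if no allogeneic blood is given in theatre, or if TXA does not change how much is given there.

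**3. Illustration of size.** The documents give no intraoperative allogeneic rate and no distribution of units, so this uses proportions transfused and assumed theatre rates. Inputs from the documents:

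- Historical postoperative rate 33.3% (A.1).
- Relative reduction of 58.6% in the retrospective TXA study (A.1); check from B.2: (58 − 24)/58 = 0.586.

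Postoperative only: 33.3% against 33.3 × (1 − 0.586) = 13.8%. The difference is 19.5 points and the risk ratio 0.41. Power with 40 per arm is 54.0% (normal approximation, pooled variance under the null).

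Now let a further x of placebo patients be transfused only in theatre, with theatre risk ratio r. The difference not counted is x × (1 − r). Each cell shows points not counted, perioperative risk ratio, and perioperative power.

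| x (assumed) | r = 0.414 (same effect) | r = 0.7 | r = 1 (no theatre effect) |
|---|---|---|---|
| 0% | 0; 0.41; 54% | 0; 0.41; 54% | 0; 0.41; 54% |
| 5% | 2.9; 0.41; 62% | 1.5; 0.45; 56% | 0; 0.49; 49% |
| 10% | 5.9; 0.41; 70% | 3.0; 0.48; 58% | 0; 0.55; 46% |
| 15% | 8.8; 0.41; 77% | 4.5; 0.50; 61% | 0; 0.60; 43% |

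Example, x = 10% and r = 0.414: 0.10 × 0.586 = 5.9 points. The perioperative difference is 19.5 + 5.9 = 25.4 points, and 5.9/25.4 = 23% of it goes uncounted.

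The absolute difference is understated only when TXA reduces theatre transfusion. The risk ratio is the same in either window when the relative effect is equal. The table does not model theatre units replacing ward units.

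**The case against.** The strongest reply is that this is a matter of wording. A.1 states the objective as postoperative, in agreement with A.5, C.3(g) and section D. Theatre units are recorded, and the Outcome Measures text says they go to analysis. The unit count in the blood-loss formula has no time limit, so on its face the primary outcome includes them. Cell-saver volume is a separate tested outcome that reflects bleeding in theatre. The protocol also uses the word postoperative loosely: A.4 applies it to a blood loss measured from preoperative hemoglobin. Finally, if TXA had no effect in theatre, the wider outcome would move the risk ratio toward 1 and lower power, as the last column of the table shows.

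Much of this stands. A reader might infer that theatre units enter no analysis at all, that the TXA effect on transfusion is definitely diluted or biased toward zero, or that the trial cannot answer its transfusion question. The documents support none of these. The primary formula may use the units, no theatre rate is given, every case uses a cell saver, and the question as A.1 words it can be answered.

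The reply does not remove the mismatch. The Outcome Measures sentence names no test, and section D lists transfusion for testing only as postoperative. The operating room list and the Outcome Measures sentence both treat the intraoperative period as separate, so loose usage cannot be relied on. A.2 and Hypothesis 2 remain wider than what is tested.

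**Conclusion.** The point holds as a minor improvement to a secondary outcome. Followed literally, the plan tests a narrower quantity than its secondary objective and Hypothesis 2, and the wider quantity promised under Outcome Measures has no specified test.

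The absolute difference in units may be understated if TXA reduces theatre transfusion. No size can be derived. In the illustration it runs from 0 to 8.8 percentage points for assumed theatre-only rates of 0% to 15%, and it is 0 throughout if TXA has no theatre effect. These figures are proportions standing in for units, and they apply a relative reduction from a study whose transfusion window the documents do not state. A firm claim of bias toward zero would go too far.

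The primary analysis, the sample size and the interim rule are untouched.

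**What to change.** In A.5, in the Outcome Measures text of C.3(g) and in the Data Analysis text of section D, define the tested transfusion outcome as total perioperative allogeneic red-cell units per patient: intraoperative plus postoperative to discharge, excluding cell-saver reinfusion. State that each unit is counted once, because the inpatient count in the electronic record list may already include theatre units. Report postoperative-only units as a descriptive breakdown, and bring the wording of A.1 into line. Make the change before any unblinded data are seen.

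The cost is wording only, since both sources are already collected. One small downside is that the total is not directly comparable with the historical 33.3% postoperative rate; the breakdown provides the postoperative count for that purpose.
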